Lower limbs venous compression has been demonstrated to effectively decrease hypotension among women undergoing scheduled cesarean section (Cyna, Andrew, Emmett, Middleton, & Simmons, 2006; Goudie, Winter, & Ferguson,, 1988; Rout, Rocke, & Gouws, 1993; Sun et al., 2004; Van Bogaert, 1998). To date, only one study has examined the use of lower limbs venous compression to decrease hypotension in laboring women and found a significant reduction in maternal hypotension with the use of SCDs. This study compared women who used SCDs to a historical comparison group of women who received care before SCDs were provided and found a decrease in the incidence of maternal hypotension from 23.3% in the comparison group to 3.23% in the SCD group. and the researchers suggest a prospective randomized trial to investigate the phenomenon (Peyronnet et al., 2017). The purpose of this study is to build upon this preliminary work and to use a randomized controlled trial to examine the effectiveness of SCDs in preventing hypotension among a larger sample of laboring women who receive an epidural analgesia.

Research Plan

• Study Design

- This study will use a randomized, non-blinded, controlled design with two arms:
 - Arm 1: Patient will receive 1L of LR and have SCDs applied 15 minutes before epidural placement and will be removed 1 hour after epidural placement
 - Arm 2: Patient will receive 1L of LR during and after epidural placement with no use of SCDs

• Setting for the study

The study will take place on Bethesda North Hospital's Labor and Delivery Unit. This unit houses 12 labor rooms and provides care to approximately 10-12 laboring women each day.

• Participants

The study will enroll 120 women who meet the following inclusion/exclusion criteria:

Inclusion Criteria:

- \circ $\;$ Laboring at Bethesda North Hospital Labor & Delivery Unit
- Will receive epidural analgesia
- 37+ weeks gestation
- Singleton pregnancy
- Category 1 tracings only before epidural placement

Exclusion Criteria:

- Under 18 years old
- Does not speak English
- o Unable to consent to involvement in the research study
- Diagnosed with fetal demise
- Diagnosis of pre-existing hypertension
- Diagnosis of gestational hypertension

- Diagnosis of pre-eclampsia
- Diagnosis of diabetes
- Breech presentation
- Contraindications to lower leg compression (ex: fractured bones in leg, cellulitis, lower limb amputation, etc.)
- Contraindications to receiving 1L of LR

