In addition to the group assignment, the envelope will include a data collection form. Data will be recorded directly on this form during the patient's visit. The form will collect the following information:

- \circ Whether patient was assigned to the SCD group or the standard care group
- Patient demographics including age, weight, and # pregnancies and # births
- Threshold systolic blood pressure (20% decrease from baseline) The study team nurse will calculate threshold systolic blood pressure by calculating the admission systolic blood pressure multiplied by 0.8
- \circ Biomed number of SCD machine (SCD group only)
- Leg measurement for SCD boot size determination (SCD group only)
- Size of boots placed (SCD group only)
- Biomed number of boots placed (SCD group only)
- Time SCDs placed on (SCD group only)
- o Time of epidural placement
- Whether patient received 1L of LR
- Time SCDs removed (SCD group only)
- Did the RN have to perform any interventions to address decreased fetal heart rate during the 1 hour after epidural placement? Yes/No
- Did the anesthesia provider treat the maternal blood pressure during the 1 hour after epidural placement? Yes/No
- All BPs and times of maternal blood pressures with SBP<90 or >20% decrease from baseline within the 1 hour after epidural placement

After delivery, the RN will complete the data collection form and place the signed informed consent form and data collection form in a locked room designated for study materials.

On the data collection forms, RNs are instructed to call a member of the study team immediately if there are any safety concerns related to the SCDs. If the study team receives a call about a safety concern, recruitment and enrollment of new participants will stop until the study team meets and reviews the incident and determines it is safe to continue. Any adverse events and serious adverse events will be reported to the IRB in compliance with IRB safety policies.

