Weekly, the research specialist will collect the data collection forms. The research specialist will review the data collection forms and compile the medical record numbers for any patient who the RN marked "yes" to "Did the RN have to perform any interventions to address decreased fetal heart rate?" The research specialist will send two study team nurses the compiled list for the week to conduct a review of the medical records of the patients requiring interventions to address decreased fetal heart rate. The same two study team nurses will review all charts throughout the study and they will separately determine category of the fetal heart tracings and send them to the research specialist. The two study team nurses assigned to determine tracing categories will be blinded to which group the patient was in. The

research specialist will conduct interrater reliability each week and any discrepancies will be sent back to the two raters to review together and come to a consensus on category assignment.

• Intervention or experimental aspect of the study

Patients randomized to Arm 1 will have SCDs placed on their lower limbs 15 minutes before the epidural placement and they will be removed one hour after epidural placement. SCD use is in the Epic order set for laboring patients but is rarely used in practice on the unit. The SCD in clinical use at Bethesda North Hospital is the Kendall SCD Express Sleeves, knee length 700 series, Ref: 29525. In this study, the study team is using the device according to the indicated description "as the sleeves/cuffs compress the legs/feet, veins collapse, forcing the blood to move upward towards the heart" but not for the indicated outcome of "prevention of DVTs"; instead the study is testing the use of this device for a new indication – for prevention of maternal hypotension.

Patients randomized to Arm 2 will receive standard care.

• Statistical Analysis

Data recorded on paper data collection forms will be entered into a password protected database. Only study team members will have access to the database. No personal information will be entered into the electronic database. Data will undergo range checks when entered into the database, and quality control procedures will be performed to ensure accuracy of the data in the electronic database.

Statistical analyses will be performed using Intellectus Statistics statistical software. The following analyses will be performed to address each hypothesis:

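### The primary outcome comes from an arm-labelled nurse form that lists only low blood pressures, and no check against the charted readings is described

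*Combined protocol and SAP*

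**What the plan says.** Under Study Design: "This study will use a randomized, non-blinded, controlled design with two arms". Maternal hypotension is the primary outcome (Sample Size Determination). Hypothesis 1 defines it as a systolic pressure under 90 mmHg or a drop of more than 20% from baseline. The Data Collection section takes the baseline from the admission systolic pressure.

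Data Collection ties the outcome record to the allocation: "In addition to the group assignment, the envelope will include a data collection form". The first item listed for the form is "Whether patient was assigned to the SCD group or the standard care group", and several later items apply to the SCD arm only. For blood pressure after the epidural, the form asks for "All BPs and times of maternal blood pressures with SBP<90 or >20% decrease from baseline within the 1 hour after epidural placement". It also has a Yes/No item on whether anesthesia staff treated the mother's pressure in that hour. On timing, the section says "Data will be recorded directly on this form" during the visit, and then "After delivery, the RN will complete the data collection form".

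Medical-record review is described for Hypothesis 2 only. Two study team nurses "conduct a review of the medical records of the patients requiring interventions to address decreased fetal heart rate", and "The two study team nurses assigned to determine tracing categories will be blinded to which group the patient was in". The Statistical Analysis section adds range checks at data entry and unspecified quality control of the electronic database.

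**The concern.** The person filling in the form knows the arm, and the unit's nurses have been taught the study's purpose (Data Collection). The form records only positive findings. A woman with no entry may have had six normal readings, one normal reading, no reading, or a low reading that nobody wrote down, and the form does not separate these cases. No measurement interval for the hour is given, so the arms could also differ in how often pressure was taken.

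The Hypothesis 1 chi-square test compares the proportions of women with an event. If events are missed equally in both arms, the test loses power but keeps its error rate. If they are missed unequally, a difference can be created or hidden. The form's contents would give little basis for telling these situations apart.

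**Working it through.** **1. What each source could reveal about a missed low reading**

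- *The low-pressure list:* entries present can be checked, because values and times are given. Absent entries leave no trace.
- *The anesthesia-treatment item:* a Yes with an empty list flags a possible missed event. It does not help with untreated episodes, it sits on the same form, and no reconciliation is described.
- *Chart review:* limited to women whose nurse reported acting on a fetal heart rate problem, and used to assign tracing category.
- *Range checks and database quality control:* aimed at what was entered. A comparison with the chart is not described.

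**2. The plan's own figure**

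Inputs from Sample Size Determination: p1 = 0.233, p2 = 0.0323, alpha 0.05 (two-sided assumed), power 0.80. The pooled formula without continuity correction is

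n = [1.96·√(2·p̄·(1−p̄)) + 0.8416·√(p1(1−p1) + p2(1−p2))]² / (p1−p2)², with p̄ = 0.13265.

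n = (0.9402 + 0.3856)² / 0.2007² = 1.7579 / 0.04028 = 43.6, so 44 per group.

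The stated 44 is reproduced. The point is about ascertainment, not sample size.

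**3. What unequal recording would do at 60 per arm**

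The documents give no recording fraction, so the fractions f are assumptions. The outcome is counted per woman: an event is lost only if every qualifying reading in that woman goes unrecorded.

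With x control and y SCD events recorded, X² = 120(x−y)² / [(x+y)(120−x−y)], significant if above 3.841. Probabilities come from summing the two binomial distributions exactly. Expected events at 23.3% are 60 × 0.233 = 14.0 per arm, so missing 10%, 20% or 30% means about 1.4, 2.8 or 4.2 women.

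| Share of events recorded (f) | No true effect, loss in SCD arm only: P(significant, favours SCDs) | No true effect, equal loss in both arms: P(significant, favours SCDs) | Planned effect, equal loss: power | Planned effect, loss in control arm only: power |
|---|---|---|---|---|
| 100% | 2.6% | 2.6% | 94% | 94% |
| 90% | 5.0% | 2.5% | 91% | 89% |
| 80% | 9.2% | 2.4% | 87% | 82% |
| 70% | 15.8% | 2.4% | 82% | 72% |

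The event rates used are 0.233 against 0.233f (second column), 0.233f in both arms (third), 0.233f against 0.0323f (fourth) and 0.233f against 0.0323 (fifth). With no true effect and loss in the control arm only, the second column applies in favour of control. These are figures for a single analysis; the planned interim looks are a separate matter and are left out.

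**The case against.** The cut-off is numeric, so there is no judgement to blind. Data are recorded during the visit, and every qualifying pressure is to be listed with its time. A woman with repeated low readings has to be missed at each of them before she drops out of the count, and a treated episode should show in the anesthesia item. The form itself is not in the documents, the research specialist reviews forms weekly, and the quality control procedures are not spelled out, so silence does not prove that no check exists. The one-sided losses in the table are invented.

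Much of this stands. The remaining risk is selective measurement or transcription, not interpretation. The anesthesia item is a real, though partial, safeguard. The most that can be said is that no check against charted pressures is *described*. The weekly review is described only as a way of finding women for tracing review.

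A reader might infer that the result will be biased towards SCDs. The documents do not support that: nothing in them shows unequal recording, and a loss in the control arm would work the other way. Nor do they support saying that a missed event could never be detected, given the anesthesia item.

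**Conclusion.** The gap is real and worth closing. As described, the primary outcome depends on equal and complete recording by staff who know the arm, and the plan offers only a partial means of showing that this was achieved. The table's size depends on three things: the assumed fractions, loss confined to one arm, and whole women being missed rather than single readings. Under those conditions, losing about three of 14 expected events in the SCD arm more than triples the chance of a false result in its favour (2.6% to 9.2%). If omission is equal, the false-positive chance barely moves and the cost is power.

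A reader might also link this to the Background section's different definition of hypotension, which uses a diastolic limit. Hypothesis 1 and the form agree on the systolic criterion, so that is a separate wording point to reconcile and not evidence of uneven ascertainment.

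**What to change.** - For every randomised woman in both arms, extract from the medical record the admission systolic pressure and all timed systolic pressures from 0 to 60 minutes after epidural placement.
- Derive the Hypothesis 1 event by a fixed rule run without arm labels. Leave the definition and the admission baseline unchanged.
- Report the number of readings per woman by arm, and the agreement between record and form.
- Check every woman with anesthesia treatment marked Yes but no low pressure listed.

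The cost is record extraction for up to 120 women by existing study staff and a few sentences in the plan, assuming pressures are charted. The present chart review covers only some women and only tracings, so this is additional work. It can also be done for women already enrolled. Its limit should be stated in the plan: extraction recovers readings that were charted but not transcribed. It reveals unequal measurement between arms but does not correct it, and it cannot recover pressures never taken.

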- Blood pressure on admission SBP>160 or DBP>110
- Fetal heart rate abnormalities before epidural

Sample Size Determination: A power analysis was conducted using the primary outcome variable, maternal hypotension, with an expected difference similar to that found in the Peyronnet and colleagues' (2017) study (3.23% vs. 23.3%) (0.3), power of 0.8, and level of significance 0.05. It was determined that 44 patients would be needed in each group, for a total sample size of 88 patients. To allow us to also examine the impact on occurrence of infant Category 2 tracings and to allow for the possibility of removing participants from the final analysis due to missing data, we plan to enroll 120 patients (60 in each group).

• Data Collection

Before the study begins, information about the study will be provided to the providers. Providers who agree with involvement of their patients will be provided a hand-out about the study to give to their patients during prenatal visits and asked to mention to their patients that they may be approached about involvement of the study when they are admitted. The nurses on the L&D unit will be provided with education about the study purpose, exclusion criteria, and procedures. All nurses on the L&D unit have received training in the proper use of SCDs clinically. However, to validate and reinforce this knowledge, the nurses on the L&D unit will be provided education on proper measurement to determine boot size for SCDs and proper boot placement and SCD use. Nurses will be instructed to call a member of the study team immediately if any safety concerns occur related to the SCDs.

When a patient who meets the inclusion/exclusion criteria is admitted, a nurse will describe the study, answer any questions the patient has, and if the patient wants to enroll in the study, the study team nurse will review the information consent form. After the patient provides written informed consent, the nurse will remove the next envelope out of a box of prefilled and sealed opaque envelopes. The envelope will provide the Subject ID number to be used on all study-related documentation and the study Arm that the patient has been randomized to, either:

- 1. SCD Group + Fluid Bolus
- 2. Fluid Bolus Group (no SCD)

These envelopes will be filled using a computerized simple random number generator (1:1 randomization) prior to the start of the study.

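### Beyond the first-hour blood pressure and fetal heart rate items, the plan describes no arm-neutral collection of adverse events, so other harms cannot be validly compared by arm

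*Combined protocol and SAP*

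**What the plan says.** The safety prompt appears twice under Data Collection. In the paragraph on nurse education: "Nurses will be instructed to call a member of the study team immediately if any safety concerns occur related to the SCDs". In the paragraph on the form: "RNs are instructed to call a member of the study team immediately if there are any safety concerns related to the SCDs". A call about a safety concern pauses enrollment until the study team has reviewed the incident.

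The reporting commitment follows directly and is wider: "Any adverse events and serious adverse events will be reported to the IRB in compliance with IRB safety policies".

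The listed form items include three that bear on safety and apply to both arms, whatever the suspected cause. Two are Yes/No questions about the first hour: one on nursing action for a falling fetal heart rate, the other on anesthesia treatment of the mother's pressure. The third is a record of low readings: "All BPs and times of maternal blood pressures with SBP<90 or >20% decrease from baseline within the 1 hour after epidural placement".

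The list has no adverse event item. It has the time the SCDs came off (SCD group only) but not the reason. Charts are reviewed only for women who had a fetal heart rate intervention, in order to categorize the tracing. The Statistical Analysis section covers hypotension and Category 2 tracings and plans no table of harms.

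Study Design describes the trial as non-blinded and the control arm as follows: "Arm 2: Patient will receive 1L of LR during and after epidural placement with no use of SCDs". The section on the intervention says of the device that "instead the study is testing the use of this device for a new indication".

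**The concern.** The commitment to report covers any adverse event, but the only described way for the team to learn of one is a call that presupposes a link to the SCDs. That makes ascertainment depend on the arm and, within Arm 1, on the judgment of a nurse who knows the assignment.

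The trial tests the device for a new indication. If it shows less hypotension, the next question will be what harms came with that benefit. For events outside the three first-hour items, the plan as written could offer only a count of calls from one arm. A low count would not show that events were few, and there would be no comparable count from Arm 2. These data cannot be reliably recovered after the trial.

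**Working it through.** **1. Is there a plan figure to reproduce?** None on safety. The point rests on reading the sections against each other; the arithmetic in steps 3 and 4 only gives scale.

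**2. Routes by which an event could be recorded, by arm**

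| Route | Arm 1 | Arm 2 | Needs attribution to SCDs? |
|---|---|---|---|
| Nurse's call (Data Collection) | Yes | Cannot apply: no SCDs worn | Yes |
| Low blood pressures, first hour (form) | Yes | Yes | No |
| Anesthesia treatment of blood pressure, first hour (form) | Yes | Yes | No |
| Fetal heart rate intervention, first hour (form) | Yes | Yes | No |
| Chart review | Only after a fetal heart rate intervention | Same | No |
| General adverse event item | Not listed | Not listed | n/a |
| Reason for early SCD removal | Not listed | n/a | n/a |
| Harms table (Statistical Analysis) | Not planned | Not planned | n/a |

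The three arm-neutral items are largely the efficacy outcomes and their management. For every other kind of event, the first row is the only described prompt, and it differs by arm by construction.

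**3. What systematic collection would support.** Input: 60 women per arm (Sample Size Determination). With x = 0 events, the exact one-sided 95% upper bound solves (1 − p)^60 = 0.05:

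- p = 1 − 0.05^(1/60) = 0.0487, or 4.9%.
- The upper end of a two-sided 95% interval is 1 − 0.025^(1/60) = 0.0596, or 6.0%.

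If the trial stopped at the first interim look, at about one third of enrollment (60/3 = 20 per arm), the one-sided bound would be 1 − 0.05^(1/20) = 13.9%.

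These bounds hold only if every woman is asked. They need no assumed capture rate.

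**4. Illustration of incomplete capture.** The documents give no capture rate c and no event rate, so the values below are assumptions. With zero reports in 60, the upper bound becomes 4.87%/c. The chance of no report at all when the true rate is 5% is (1 − 0.05c)^60.

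| Capture c (assumed) | Upper bound with zero reports | Chance of no report at a true 5% rate |
|---|---|---|
| 1 | 4.9% | 0.95^60 = 4.6% |
| 0.5 | 4.87/0.5 = 9.7% | 0.975^60 = 21.9% |
| 0.25 | 4.87/0.25 = 19.5% | 0.9875^60 = 47.0% |

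The table shows the direction and possible scale of the loss. It does not estimate what would happen in this trial. Capture of device concerns, which nurses are told twice to phone in, could be much better than capture of other events.

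**The case against.** The strongest reply is that a reader might infer from the call rule that no harms are collected without attribution to the device, or that nothing can be compared by arm. The documents contradict that. The same form records low blood pressures, blood pressure treatment and fetal heart rate interventions in both arms for an hour, and these include the maternal and fetal problems that the protocol is chiefly concerned with. That part of the reply stands, and it is why the point is confined to other harms.

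A reader might also infer that the plan cannot keep its commitment to the IRB. That goes too far. The commitment is not limited by arm or cause and relies on IRB policies that are not in the documents, so other events may be reported ad hoc. The form itself is not reproduced either, and it carries the call instruction, which is not among the listed items, so the list may be incomplete. What can be said is that no collection step is described.

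Nor do the documents support the complaint that an enrollment pause lacks an Arm 2 rate to judge it against. The pause is a review of one incident, and a concern specific to the device has no counterpart in Arm 2.

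In mitigation, the device is already in clinical use at the hospital and in the order set for laboring patients, though rarely used on the unit. Women with contraindications to leg compression are excluded, and planned wear is short. This lowers the expected risk but does not supply the missing data.

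Finally, a harms table with 60 per arm will settle little: 3 events against 0 gives a two-sided Fisher p of 0.24. That is correct, and the table should be described accordingly.

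**Conclusion.** The point holds in a limited form. Outside the three first-hour items, the plan describes no systematic collection of adverse events that works the same way in both arms. Its one stated prompt cannot operate in Arm 2 and in Arm 1 depends on attribution by an unblinded nurse. A comparison of other harms by arm would therefore be biased by ascertainment, and the commitment to report any adverse event lacks a described step for finding them.

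The primary test of hypotension is unaffected. The only figure that needs no assumed capture rate is the 4.9% one-sided upper bound for 0 events in 60 women, all asked; the number of calls cannot support that statement. The bounds of 9.7% and 19.5% rest on assumed capture of 50% and 25%, and the conclusion does not depend on them. It does assume that the listed form items are complete. If the actual form already has a general adverse event item for both arms, the protocol should say so, and only the table would be missing.

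**What to change.** 1. **Form, both arms.** Add one item under Data Collection, answered for every woman whatever the suspected cause: any adverse event from 15 minutes before the epidural to 1 hour after it, Yes/No, with type and time. Include a short definition of what counts, because without one the answer still turns on an unblinded nurse's judgment.
2. **Form, Arm 1.** Next to the existing SCD removal time, record the reason for any early removal.
3. **Immediate call.** Leave the instruction as it is.
4. **Statistical Analysis.** Add a descriptive table of adverse events by randomized arm with exact confidence intervals, and state that it is not a powered comparison.

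The cost is two entries on a paper form that is already completed for every woman, and one table. The downside is that some labor events unrelated to the device will be recorded. Showing both arms side by side lets a reader see that background, but with 60 per arm the table remains descriptive only.

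### Category 2 tracings are read only if an unblinded RN reported an intervention, so the incidence in Hypothesis 2 is not measured and missed cases cannot be counted by arm

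*Combined protocol and SAP*

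**What the plan says.** Hypothesis or Research Question and Statistical Analysis both frame Hypothesis 2 as a lower incidence of Category 2 tracings with SCDs. It is tested by chi-square between the arms at 0.05. Sample Size Determination gives this outcome as one reason for enrolling 120 women rather than 88 ("To allow us to also examine the impact on occurrence of infant Category 2 tracings").

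Data Collection describes how tracings reach the raters:

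- The form asks "Did the RN have to perform any interventions to address decreased fetal heart rate during the 1 hour after epidural placement? Yes/No".
- Each week the research specialist is to "compile the medical record numbers for any patient who the RN marked" yes on that item. Two study team nurses receive the list and "conduct a review of the medical records of the patients requiring interventions to address decreased fetal heart rate".
- The next sentence says "The same two study team nurses will review all charts throughout the study". These raters "will be blinded to which group the patient was in".

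The RN is not blinded. Study Design calls the trial non-blinded, and the form the RN completes records "Whether patient was assigned to the SCD group or the standard care group". Data Collection adds that "The nurses on the L&D unit will be provided with education about the study purpose, exclusion criteria, and procedures".

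Nothing provides for a woman marked no to have her tracing read, sampled or checked, and the form has no field for tracing category.

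**The concern.** A Category 2 tracing counts only if the RN intervened for a decreased heart rate, marked yes, and the raters then agreed on the category. A Category 2 tracing without a recorded intervention is lost. Blinding the raters protects how a strip is classified, but not which strips they see.

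Two consequences follow. If the RNs capture the same share of Category 2 tracings in both arms, incidence is understated and power is lost. If they capture different shares, which an open design permits but the documents do not show, the comparison is biased, in either direction.

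This outcome is not primary, but a significant difference in it can end data collection at either interim look. Biased capture could therefore also cut short Hypothesis 1.

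**Working it through.** **Inputs from the protocol.** 60 women per arm; chi-square at 0.05; interim looks at about one third and two thirds of enrolment, that is 60 × 1/3 = 20 and 60 × 2/3 = 40 per arm, stopping on either outcome.

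**The plan's own figure.** The only sample size given is for hypotension. For 3.23% vs 23.3%, with mean 13.265%, two-sided 0.05 and power 0.8: n = [1.96·√(2 × 0.13265 × 0.86735) + 0.8416·√(0.0323 × 0.9677 + 0.233 × 0.767)]² / 0.2007² = 43.6, so 44 per group, as stated. Sidedness is not given, but the two-sided test without continuity correction reproduces 44, so it is used below. The plan has no corresponding figure for Category 2.

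**Assumptions.** True Category 2 rates and capture (the share of Category 2 tracings that are flagged) are mine. Unread women count as non-events. Statistical Analysis does not say so, but this is the more natural reading, because whole arms are compared and only women with Category 1 tracings before the epidural are admitted.

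**Model.** Confirmed rate = true rate × capture. Counts are binomial with n = 60. Reject when |x₁ − x₂|/60 ÷ √[p̄(1 − p̄) × 2/60] > 1.96, where p̄ is the pooled rate. Probabilities are exact sums over all pairs of counts, for a single test unless stated.

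**1. Equal capture, no true effect.** At 60% or 70% capture and true rates of 20% to 60%, the false-positive rate is 4.7% to 5.3%.

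**2. Equal capture, true effect: power.**

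| True rates | all read | 90% | 80% | 70% | 60% |
|---|---|---|---|---|---|
| 40% vs 20% | 0.68 | 0.62 | 0.55 | 0.48 | 0.40 |
| 30% vs 15% | 0.51 | 0.46 | 0.40 | 0.34 | 0.29 |
| 50% vs 25% | 0.82 | 0.75 | 0.68 | 0.60 | 0.51 |

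**3. Unequal capture, no true effect: false-positive rate (%), by true rate.**

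| Capture, control/SCD | 20% | 30% | 40% | 50% | 60% |
|---|---|---|---|---|---|
| 95/90 | 5.1 | 5.7 | 5.6 | 6.3 | 6.7 |
| 90/85 | 5.0 | 5.7 | 5.6 | 6.2 | 6.8 |
| 70/65 | 5.0 | 5.5 | 6.0 | 6.1 | 6.4 |
| 70/60 | 5.9 | 6.9 | 8.2 | 9.2 | 10.4 |
| 70/50 | 10.0 | 13.3 | 18.0 | 22.9 | 27.8 |
| 70/40 | 17.9 | 25.6 | 36.0 | 46.5 | 56.4 |

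Swapping the arms gives the same rates, with the false result against SCDs.

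**4. Bias can hide an effect.** For true 40% vs 20% at 60/70 capture, the confirmed rates are 24% vs 14% and power is 0.28, against 0.48 at 70/70.

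**5. Why flag and confirmation rates by arm do not settle it.** No effect with unequal capture: 0.40 × 0.7 = 28% and 0.40 × 0.5 = 20%. Real effect with equal capture: 0.40 × 0.7 = 28% and 0.286 × 0.7 = 20%. Both give about 17 vs 12 confirmed cases (60 × 0.28 = 16.8; 60 × 0.20 = 12).

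**6. Interim stopping on Category 2 alone.** Looks are at 20 and 40 per arm, each at 0.05, with a true 40% in both arms. With every strip read, the chance of stopping is 8.4%; that part belongs to the uncorrected stopping rule. Selective reading adds 0.1 points at 70/70, 0.5 to 0.6 for 5-point gaps, 2.2 at 70/60, 9.0 at 70/50 and 21.5 at 70/40. The 70/50 addition ranges from 4.0 points at a true 20% to 16.1 at a true 60%.

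**The case against.** **The raters are said to review all charts.** That sentence directly follows the one that sends them the weekly list, and no other charts are sent to them. If every enrolled woman is meant, the two sentences conflict and still need correction.

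**The raters are blinded, rate separately and must confirm each event.** True, so a yes from the RN cannot create an event alone. Confirmation removes false flags but cannot recover tracings that were never sent.

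**No bias has been shown.** This stands. The documents give no ground for expecting a particular gap, and a 5-point gap does little. The large figures need gaps of 20 points or more.

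**Reading every strip need not gain power.** Suppose 40% of controls have Category 2, with 28% drawing intervention and 12% not, and SCDs halve only the first group. The selected endpoint (28% vs 14%) has power 0.48, and the full one (40% vs 26%) has 0.38. The arithmetic is right, but capture there is 28/40 = 70% versus 14/26 = 54%. It is a case of unequal capture and does not contradict the loss under equal capture. It does show that the power figures must be read with that condition.

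**The outcome is secondary and enrolment may be well advanced.** Both points are fair. The protocol is dated December 2022, with a start date in February 2021 and three months of data collection planned. This limits the severity and bears on cost, but leaves the mismatch in place.

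**Conclusion.** The concern holds. The endpoint collected is an RN-reported intervention followed by rater-confirmed Category 2, which is narrower than the incidence in Hypothesis 2, and the RN who controls entry to it is unblinded. That much rests on the text alone.

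The size of the harm rests on assumed rates. Equal capture leaves the false-positive rate near 5% and costs power. A small capture gap matters little; a gap of 20 points or more matters a lot. The main weakness is that the planned data could not show which situation the trial is in. This should be fixed, but because the outcome is not primary it does not by itself undermine the main comparison, except through the interim rule.

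**What to change.** Have the same two blinded raters classify the one-hour post-epidural tracing of every randomised woman, including those already enrolled, supplied by Subject ID without arm information. State the one-hour window in Hypothesis 2, since at present it appears only in the form item. Use all randomised women as the denominator and report a woman without a readable strip as missing. Keep the RN's answer as a separate descriptive item, and report by arm the share of rater-read Category 2 tracings that the RN had flagged. That makes differential flagging visible.

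The cost is up to 120 one-hour strips instead of a subset, plus a new step in which the research specialist extracts each strip and relabels it by Subject ID. Tracings are already read afterwards from the medical record, so no new staff or patient contact is needed. If enrolment is advanced, most of the reading would be retrospective, and the documents do not say whether past strips remain available.

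If this is not done, restate Hypothesis 2 as intervention-triggered, rater-confirmed Category 2 over all randomised women. Count no as a non-event and a blank as missing, and state that differential flagging cannot be excluded. That costs only wording.

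Separately and optionally, report any Category 3 tracings alongside, without redefining the Category 2 hypothesis.
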